Merotocin nasal spray (400 µg intra-nasally per dose, divided into 2 sprays with 1 spray in each nostril) administered 6 to 8 times every treatment day. Placebo nasal spray administered 6 to 8 times every treatment day.

The active IMP is a stock solution consisting of merotocin dissolved in an isotonic citrate/phosphate buffer of pH 5.5 at a concentration of 2 mg/mL. The placebo IMP is an isotonic citrate/phosphate buffer solution of pH 5.5. The IMPs are identical in appearance.

DURATION OF TREATMENT

Maternal subjects will be exposed to either merotocin or placebo for 14 days.

STATISTICAL METHODS

All statistical tests will be two-sided, using a 5% significance level. All statistical analyses will be performed using SAS software (SAS Institute, Inc, Cary, North Carolina) (Version 9.2 or later). The analysis of efficacy will be performed for the FAS and per protocol (PP) analysis set.

The primary analysis will be performed using the FAS, defined as all randomized and exposed maternal subjects providing data on volume of MoM produced for at least 1 day after dosing initiation. The FAS will be analyzed according to the actual treatment received. Analysis performed using the PP analysis set, defined as all randomized maternal subjects without major protocol deviations, will be considered supportive.

Primary Endpoint: Primary Analysis

The primary objective of this proof of concept (PoC) trial is to evaluate the effect of merotocin on increasing milk production in women with preterm delivery. The primary endpoint of the trial

is the volume of MoM produced over Days 1 to 14.

Repeated Measures ANCOVA Model:

The primary endpoint will be analyzed using a repeated measures ANCOVA with a general (unstructured) covariance matrix. The daily volume of MoM produced will be the dependent variable. The model will include the baseline volume of MoM produced as a covariate, with treatment group, treatment day, treatment-by-day interaction, and gestational age group (<27 weeks and \geq 27 weeks) as factors. The baseline volume of MoM produced is defined as the volume obtained at the 24-hour interval for eligibility during the observation period. The average treatment effect across treatment days and the within-day treatment effect will be reported along with the corresponding two-sided 95% confidence intervals and p-values.

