The present trial is the first investigation in the target population of women with preterm labor and the first investigation with merotocin exposure beyond 45 hours. The proposed dosing regimen is 400 µg intra-nasal dose (divided into two sprays of 200 µg each) administered 6 to 8 times every 24 hours. The nasal spray can be used at consecutive sessions at least two hours apart for a maximum of 8 times every 24 hours. In the multiple ascending dose part of the phase 1 trial, the harmonic mean terminal half-life ($t_{1/2}$) with the 400 µg intra-nasal dose was 0.56 hours. With this $t_{1/2}$, merotocin concentrations are negligible at two hours after dosing (3.6 half-lives) and merotocin is considered to be eliminated at three hours after dosing (5 half-lives).

Regarding exposure of merotocin to the infants, transfer of merotocin from blood to breast milk was not observed in the phase 1 trial in healthy postpartum women specifically investigating this

risk, as the concentration of merotocin in the milk of all subjects was below the lower limit of quantification. Milk samples obtained in the present trial will also be evaluated for merotocin.

The blood sampling performed as part of the trial might be associated with mild discomfort, bruising, and a very rare risk of infection.

In conclusion, the evaluation of the benefits and risks indicates that participation in this trial is associated with a favorable benefit-risk ratio.

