5 TREATMENTS

5.1 Treatments Administered

5.1.1 Investigational Medicinal Products

The IMPs of the trial include merotocin nasal spray and placebo nasal spray.

Eligible maternal subjects will be randomly assigned in a 1:1 ratio to receive either merotocin nasal spray (400 µg per dose, divided into 2 sprays with 1 spray in each nostril) or placebo nasal spray. Maternal subjects will use their assigned nasal spray a maximum of 8 times every 24 hours (a maximum daily dose of 3200 µg) from the time of randomization for 14 treatment days (i.e., Days 1 to 14). Treatment is administered intra-nasally as 1 spray in each nostril approximately 5 to 10 minutes before a milk expression session. Each single spray constitutes half a dose (200 µg) and maternal subject must administer the spray in both nostrils to receive the 400 µg dose.

Subjects should aim to express milk 6 to 8 times every 24 hours including at least once during the night and with no more than 5 hours between milk expression sessions. As the IMPs will be administered only prior to milk expression, the exact daily dose of merotocin may vary for each maternal subject on each treatment day. [Table 1](#) presents the total daily dose of merotocin administered to maternal subjects based on milk expression frequency. The IMP should be administered prior to consecutive milk expression sessions at least 2 hours apart for a maximum of 8 times per treatment day. Subjects should follow instructions on how to use the nasal spray correctly and take precautions (e.g., washing hands after IMP administration but before milk expression) to avoid potential indirect transfer of IMP into milk.

Table 1 Total Daily Dose of Merotocin by Milk Expression Frequency

Milk Expression Frequency	Total Daily Dose of Merotocin (µg)
5 times per treatment day	2000
6 times per treatment day	2400
7 times per treatment day	2800
8 times per treatment day	3200
9 or more times per treatment day	3200

In this trial, treatment days start from the time of randomization, with Day 1 being the first 24 hours after randomization, Day 2 being 24 to 48 hours after randomization and so on. The treatment period will include 14 such consecutive intervals of 24 hours from the time of randomization, corresponding to 14 treatment days (Days 1 to 14).

Maternal subjects will be exposed to merotocin or placebo for 14 days, depending on randomization.

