9.3 Protocol Deviations

Protocol deviations will be rated as either minor or major. Protocol deviations impacting the primary endpoint will be rated as major. Maternal subjects will be excluded from the per protocol (PP) analysis set from the day where the first major protocol deviations occurred and onwards. Data will not be excluded from the PP analysis set in case of minor protocol deviations. Major protocol deviations include but are not limited to the following:

- For a given treatment day:
 - Less than 5 milk expression attempts
 - Less than 80% compliance with intra-nasal administration of assigned treatment prior to milk expression

The Ferring clinical team will perform a blinded review of protocol deviations before declaration of clean file and lock of database. If the blinded review identifies serious unforeseen deviations deemed to impact the primary endpoint and affect the conclusions of the trial, these will also be rated as major deviations. A comprehensive list of major protocol deviations will be detailed and documented in the clean file document prior to database release. Major protocol deviations will be tabulated by treatment day and treatment group.

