9.7 Extent of Dosing and Treatment Compliance

Extent of actual dosing is defined as the number of intra-nasal trial treatment spray administrations and also as the number of days receiving trial treatment. Both variables will be summarized by treatment group.

Compliance is defined in terms of the number of milk expression attempts and the use of the nasal spray. For women attempting less than 6 milk expressions on a given day, their daily compliance is calculated as number of IMP administrations divided by 5 (the minimum number of milk expression attempts stated in the protocol). For women who perform 6-8 milk expression attempts, compliance is calculated as the number of IMP administrations divided by number of milk expressions. For women expressing milk more than 8 time per day, compliance is calculated as the number of IMP administrations divided by 8 (the maximum number of IMP administrations specified in the protocol). This will be done for both the overall treatment period and each treatment day. Compliance over Days 1 to 14 will be summarized by treatment group as the number of maternal subjects with at least 80% compliance.

Drug dosing will be evaluated by weighing each nasal spray bottle before dispensing and after return to the site taking into account the number of doses administered as reported by the maternal subject.

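### If the 2-hour condition in 5.1.1 and 1.3 limits dosing, the 9.7 compliance denominator for days with 6 to 8 sessions does not allow for it, and a woman who follows the limit can drop out of the supportive per-protocol set

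*Combined protocol and SAP*

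**What the plan says.** Section 5.1.1 puts two conditions on dosing in one sentence: "The IMP should be administered prior to consecutive milk expression sessions at least 2 hours apart for a maximum of 8 times per treatment day". Section 1.3 gives the same pair, "The nasal spray can be used at consecutive sessions at least two hours apart for a maximum of 8 times every 24 hours", and goes straight on to the half-life of the intranasal dose. The expression schedule (6.4.1, and Table 5 in 7.1.1) asks for 6 to 8 sessions a day with a longest gap of 5 hours. It gives no shortest gap.

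Section 9.7 sets the compliance denominator by number of sessions:

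- Fewer than 6 sessions: doses divided by 5.
- 6 to 8 sessions: "For women who perform 6-8 milk expression attempts, compliance is calculated as the number of IMP administrations divided by number of milk expressions".
- More than 8 sessions: "For women expressing milk more than 8 time per day, compliance is calculated as the number of IMP administrations divided by 8".

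The score is computed for each treatment day and for the whole period, and the period result is reported as follows: "Compliance over Days 1 to 14 will be summarized by treatment group as the number of maternal subjects with at least 80% compliance".

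Among the major deviations for a given treatment day, section 9.3 lists "Less than 80% compliance with intra-nasal administration of assigned treatment prior to milk expression". The consequence is stated there too: "Maternal subjects will be excluded from the per protocol (PP) analysis set from the day where the first major protocol deviations occurred and onwards". Section 9.3 does not cite 9.7, but 9.7 holds the only definition of daily compliance. Section 9.6.2 makes the FAS analysis primary and the per-protocol (PP) analysis supportive.

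**The concern.** The sentence in 5.1.1 can stop a woman from dosing at a session in two ways: she has already had 8 doses, or the session comes too soon after the last one. Section 9.7 takes the first kind of session out of the denominator and leaves the second kind in. A session less than 2 hours after a dosed one is compatible with the schedule. If the 2 hours limits dosing, withholding the spray there is correct conduct, yet 9.7 scores it like a forgotten dose.

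At stake is the content of the PP set. It is meant to show the effect in women treated as planned, and it is used for the primary and secondary efficacy endpoints and for the missing-data sensitivity analysis (9.6.1, 9.6.2). It should not lose days on which the dosing rule was followed.

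**Working it through.** **Plan's own figure.** Table 1 in 5.1.1 links sessions to daily dose. With 400 µg per dose, 400 × min(sessions, 8) gives 2000, 2400, 2800, 3200 and 3200 µg for 5, 6, 7, 8 and 9 or more sessions, which matches the table. So Table 1 also recognises the 8-dose maximum and has no entry for a session left undosed because of the 2-hour condition.

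**Formula (9.7).** Score = doses / D, where D = 5 for fewer than 6 sessions, D = the number of sessions for 6 to 8, and D = 8 above 8. The limit in 9.3 is 80%.

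| Sessions | One dose withheld | Two doses withheld |
|---|---|---|
| 6 | 5/6 = 83.3% | 4/6 = 66.7% |
| 7 | 6/7 = 85.7% | 5/7 = 71.4% |
| 8 | 7/8 = 87.5% | 6/8 = 75.0% |
| 9 | 8/8 = 100% | 7/8 = 87.5% |

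On a day with 6 to 8 sessions, two withheld doses give a major deviation and one does not. On a 9-session day the same two withheld doses pass, because the 8-dose maximum has already lowered the denominator. One withheld dose plus one forgotten dose at 8 sessions also fails (6/8 = 75.0%), whereas one forgotten dose among the 7 sessions that could be dosed would be 6/7 = 85.7%.

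**Does such a day fit the schedule?** With two gaps of 1.5 hours, the remaining gaps average (24 − 3)/6 = 3.5 hours at 8 sessions and (24 − 3)/5 = 4.2 hours at 7. Both are under 5 hours. An 8-session example is hours 0, 3, 4.5, 8, 9.5, 13, 17 and 21, where at most 6 doses can be given 2 hours apart. At 6 sessions two short gaps can fall on a single day but cannot recur daily: two gaps under 2 hours plus four of at most 5 hours come to less than 24.

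**Is the woman within the regimen?** At 8 sessions, 6 doses (6 × 400 = 2400 µg) lie inside the regimen in the synopsis, "administered 6 to 8 times every treatment day". At 7 sessions, 5 doses do not, although the limit would have allowed no more.

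**What follows from one such day.** Over fourteen 8-session days, one 6/8 day gives (13 × 8 + 6)/(14 × 8) = 110/112 = 98.2%, so she still counts as compliant in the period summary. In the PP set, a deviation on Day d removes 15 − d days: 12 of 14 if it falls on Day 3, 8 of 14 on Day 7. Those losses come from the onwards rule in 9.3, which applies to every major deviation; 9.7 only supplies the trigger.

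**Which reading of the 2 hours?** Section 1.3 has the spray as its subject and follows the condition with a half-life of 0.56 hours and negligible concentrations at 2 hours (2/0.56 = 3.6 half-lives). That is the reasoning for a dosing interval. The 5.1.1 sentence taken alone could also describe how far apart sessions should be.

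**The case against.** The strongest reply is that 5.1.1 sets a minimum spacing of sessions, so no session on a 6-to-8-session day is ever left undosed. Table 1 fits that reading, as do the texts that ask for a dose before each session (synopsis, 3.1.2, 3.6.5, 6.4.1, Figure 1 note c). The 9.7 formula would then be right. This stands as a possible reading, and it is why the point is conditional. It does not leave the text in order, because the minimum would then be missing from 6.4.1 and Table 5.

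The trigger is also narrow. It needs two withheld doses on the same day. Pumping with immediate hand expression, or breastfeeding followed by pumping, counts as one session (7.1.1), and hand expression between pumping sessions is barred after randomization (4.3.3). The lactation manual, which is not part of the document, may also advise on spacing. All of this stands.

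Three stronger inferences are not supported:

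- A reader might conclude that 6.4.1 contradicts 5.1.1. It omits the 2-hour condition, which calls for alignment only.
- A reader might conclude that a woman who doses at all 8 sessions against the limit is sure to stay in the PP set because she scores 100%. The list in 9.3 is open, and the blinded review can still rate such dosing as a major deviation.
- A reader might carry the damage over to the main result. The primary analysis uses the FAS, to which the compliance rule does not apply.

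**Conclusion.** The point holds conditionally. If the 2-hour condition limits dosing, the 9.7 denominator for 6 to 8 sessions is inconsistent with it, and the plan can exclude a woman for following it: 5/7 = 71.4% or 6/8 = 75.0% against a limit of 80%. Nothing in the document waives that deviation; the blinded review is described as adding major deviations.

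The scope is small. Only the supportive PP analyses and the compliance summary are touched; the FAS analysis, the proof-of-concept decision and the power are not. The number of such days is not given and is probably low. The conclusion rests on the dosing-limit reading and on 9.7 being the measure that 9.3 has in mind. It is worth correcting before unblinding because it decides membership of an analysis set and the correction is cheap.

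**What to change.** In 9.7, for days with 6 or more sessions, divide by the largest number of that day's recorded sessions that could be dosed at least 2 hours apart, with a maximum of 8 and a minimum of 5. Count in the numerator only doses given at least 2 hours after the previous counted dose. List doses given inside 2 hours separately for the blinded deviation review. Keep the divisor of 5 for days with fewer than 6 sessions.

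The denominator must come from the session times and not from the doses the woman happened to take. In the 8-session example above, a woman who doses at hours 4.5 and 9.5 instead of 3 and 8 still takes the maximum of 6. If a session counted as available whenever it fell at least 2 hours after her own last dose, hours 3, 4.5, 8 and 9.5 would all count and she would score 6/8 = 75.0% again. With the largest possible number as denominator she scores 6/6 = 100%.

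Other checks of the rule:

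- Two withheld doses at 7 sessions give 5/5 = 100%, and at 6 sessions 4/5 = 80.0%, which is not below the limit.
- Two doses forgotten at 8 well-spaced sessions remain 6/8 = 75.0%.
- Two withheld and two forgotten at 8 sessions give 4/6 = 66.7%. Both of these last two are still deviations.

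State in 5.1.1 and 6.4.1 that the 2 hours is a limit on dosing. If the sponsor means a minimum spacing of sessions, keep the 9.7 formula and add that minimum to 6.4.1 and Table 5.

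The cost is a small text change and one extra derivation from session times already recorded on the milk container labels. The score also becomes somewhat more lenient on days with close sessions: 5 doses in 7 sessions can score 100% although that is fewer than 6 doses.

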9.8 Safety

9.8.1 General Considerations

Safety parameters will be evaluated for the safety analysis set.

9.8.2 Adverse Events

All AEs recorded for maternal subjects and infants will be coded using MedDRA. Maternal subject TEAEs will be tabulated by System Organ Class (SOC) and PT, and separately all infant TEAEs will also be tabulated by SOC and PT. The total number of maternal subjects reporting a TEAE, the percentage of maternal subjects (%) with a TEAE and the number of events reported will be presented.

Summary tables will be prepared for:

- All TEAEs
- TEAEs by causality (related/unrelated)
- TEAEs leading to death
- TEAEs by intensity
- Treatment-emergent adverse drug reactions by intensity
- Treatment-emergent SAEs
- TEAEs leading to withdrawal

Separate data listings will be provided for AEs for maternal subjects and infants. Pre-treatment AEs will be flagged.

9.8.3 Other Safety Variables

Physical examination data will be presented as shift tables from baseline by treatment group. Maternal subject blood pressure and heart rate will be summarized in shift tables by treatment group.

9.9 Interim Analysis

An unblinded interim analysis for futility assessment is planned once approximately 50% of the planned 100 subjects have completed assigned treatment period of Days 1 to 14 of the trial. The primary endpoint, volume of MoM produced over Days 1 to 14, will be evaluated for futility. Stopping the trial due to lack of merotocin benefit (i.e., futility) could be considered if the conditional power is lower than 10%.

The futility analysis has an impact on the overall power of the trial. A simulation study was performed to assess the power of the trial when including the proposed futility analysis. Under an alternative hypothesis of treatment effect (i.e., 50% increase), the overall power of the trial with inclusion of futility analysis is 77.2% and 91.1% and the probability of declaring futility during the interim analysis is 4.6% and 1.1% when the within subject correlation is 0.8 and 0.6, respectively. Assuming no treatment effect, the probability of declaring futility during the interim analysis is

37.0% and 31.0% when the within subject correlation is 0.8 and 0.6, respectively. In this simulation study, the conditional power was evaluated with an assumption that the future data after the interim analysis would be generated under the treatment effect of 50% increase for merotocin relative to placebo.

The interim analysis will be performed by the DMC (see Section 3.4) based on cleaned data, and the recruitment will continue at the time of interim analysis unless otherwise notified. The DMC will review unblinded interim data and make a recommendation on whether the trial should be terminated early due to the futility (non-binding).

There is no planned interim analysis with the intention to stop the trial early due to overwhelming efficacy.

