9.1 Determination of Sample Size

The primary objective of this trial is to evaluate the effect of merotocin on increasing milk production in women with preterm delivery. The comparison is based on the primary endpoint of the volume of MoM produced over Days 1 to 14.

Since neither the onset nor the duration of effect of merotocin is known, the initial sample size calculation is based on a comparison of the time-averaged difference between the merotocin group and the placebo group over Days 1 to 14. A sample size of 100 maternal subjects, allocated equally to each treatment group, will provide roughly 80% power to detect a 50% increase in the volume of MoM produced over Days 1 to 14, compared to placebo.

The primary analysis of the volume of MoM obtained over Days 1 to 14 will be based on a repeated measures ANCOVA. For a given sample size, the power is a function of the assumed (constant) treatment effect and the assumed correlation of observations within subjects. The power for a sample size of 100 maternal subjects equally distributed between the two treatment groups for various combinations of correlation and treatment effect is shown in [Table 7](#). As shown in the table, a sample size of 100 subjects has approximately 80% power to detect a 50% increase in the volume of MoM produced, unless the within subject correlation is greater than 0.8.

Table 7 Power for Various Combinations of Correlation and Treatment Effect

Correlation	Treatment effect ^a (merotocin relative to placebo)		
	30% increase	40% increase	50% increase
0.6	64.2 %	81.1 %	92.3 %
0.7	57.2 %	74.4 %	86.1 %
0.8	52.1 %	66.5 %	80.2 %

^a Assuming 100 subjects will be equally distributed between the two groups, with a uniform 30% drop-out rate in the trial.

The results presented in [Table 7](#) are based on simulations. For each scenario, 1,000 datasets with 100 subjects equally distributed between the 2 treatment groups were generated. In each simulation, 14 observations from a multivariate log-normal distribution were generated for each subject. The means and variances of the multivariate log-normal distribution used to draw samples from, were based on external data received by Ferring. The correlation between the volume of MoM expressed

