9.6.2 Primary Endpoint

Primary Endpoint: Primary Analysis

The primary objective of this PoC trial is to evaluate the effect of merotocin on increasing milk production in women with preterm delivery. The primary endpoint of the trial is the volume of MoM produced over Days 1 to 14.

Repeated Measures ANCOVA Model:

The primary endpoint will be analyzed using a repeated measures ANCOVA with a general (unstructured) covariance matrix. The daily volume of MoM produced will be the dependent

variable. The model will include the baseline volume of MoM produced as covariate, with treatment group, treatment day, treatment-by-day interaction, and gestational age group (<27 weeks and \geq 27 weeks) as factors. The baseline volume of MoM produced is defined as the volume obtained at the 24-hour interval for eligibility during the observation period. The average treatment effect across treatment days and the within-day treatment effect will be reported along with the corresponding two-sided 95% confidence intervals and p-values.

The analyses based on the FAS will be considered the primary, while the analyses based on the PP analysis set will be considered supportive. PoC will be considered to be established if the repeated measures ANCOVA model results in a significant positive average treatment effect of merotocin compared to placebo across the treatment period in the FAS.

Primary Endpoint: Sensitivity/Supportive Analyses

The Safety Committee may choose to reduce the dose in case of any safety concerns. In that case, the analyses will be performed both by combining the merotocin dose groups into one and by using the actual merotocin dose groups separately.

Sensitivity analyses exploring the impact of the missing data assumption on the results of the primary analysis will be performed for the FAS and PP analysis sets. Missing data will be imputed under a MNAR assumption using the pattern-mixture model with control-based pattern imputation.

The sensitivity of the results with respect to choice of the covariance structure will be investigated using more restrictive covariance structures (compound symmetry, Toeplitz, separate compound symmetry for each treatment group, and separate Toeplitz pattern for each treatment group). Nested models will be compared using the likelihood ratio test. In addition, interactions of treatment and gestational age group will be tested in the model with a general covariance structure.

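### Section 9.9: with the usual conditional-power formulas, the futility probabilities stated at correlation 0.8 (4.6% with the effect, 37.0% without) do not go together, and the formula, model and timing behind them are not stated

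*Combined protocol and SAP*

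**What the plan says.** Section 9.9 plans one unblinded futility look "once approximately 50% of the planned 100 subjects have completed assigned treatment period of Days 1 to 14". The rule is worded as "Stopping the trial due to lack of merotocin benefit (i.e., futility) could be considered if the conditional power is lower than 10"%, and it is non-binding. In the supporting simulation "the conditional power was evaluated with an assumption that the future data after the interim analysis would be generated under the treatment effect" of a 50% increase.

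For that 50% increase, Section 9.9 reports power with the look of 77.2% at within-subject correlation 0.8 and 91.1% at 0.6, and says that "the probability of declaring futility during the interim analysis is 4.6% and 1.1% when the within subject correlation is 0.8 and 0.6, respectively". With no effect the probability of declaring futility is "37.0% and 31.0% when the within subject correlation is 0.8 and 0.6, respectively". Table 7 in Section 9.1 gives 80.2% power at correlation 0.8 without the look.

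On the model, Section 9.6.2 specifies unstructured covariance: "The model will include the baseline volume of MoM produced as covariate, with treatment group, treatment day, treatment-by-day interaction" and gestational age group. Section 9.1 says that "the power is a function of the assumed (constant) treatment effect and the assumed correlation of observations within subjects", and describes the Table 7 runs: "For each scenario, 1,000 datasets with 100 subjects equally distributed between the 2 treatment groups were generated", with 30% drop-out built in. Section 9.9 does not state its own model, standard-error method, conditional-power formula, information fraction or number of replicates.

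**The concern.** The stated power fixes how far apart the interim statistic should lie with and without the effect. A rule that stops only 37.0% of null trials at half the information should then rarely stop a trial of an effective drug, yet 4.6% is reported. A later look would raise the 4.6% side to the right level, but would stop far more than 37.0% of null trials.

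This paragraph is the protocol's only account of how the rule behaves. If its figures describe a different analysis or timing from the one to be used, the sponsor and the DMC would misjudge both the risk of stopping an effective drug and the chance of stopping an ineffective one.

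**Working it through.** **Inputs.** Two-sided 5% test (Section 9.6.1); power at correlation 0.8 of 80.2% (Table 7) or 77.2% (Section 9.9); conditional-power cut 10%, design effect for future data, look at about half (Section 9.9); 30% drop-out (Section 9.1). The sponsor's means and variances are not given, so the drift is back-solved from the stated power: θ = 1.96 + z(power) = 2.809 at 80.2%, 2.705 at 77.2%.

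**1. Attempt to reproduce the stated pair.** With the design-drift formula, conditional power falls below 10% when the interim Z is below

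c = [1.96 − 1.2816·√(1−t) − θ(1−t)] / √t.

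Then P(stop | no effect) = Φ(c) and P(stop | effect) = Φ(c − θ√t).

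At t = 0.50:
- 80.2% power: c = (1.960 − 0.906 − 1.404)/0.707 = −0.496. This gives 31.0% with no effect and Φ(−0.496 − 1.986) = 0.65% with the effect.
- 77.2% power: c = (1.960 − 0.906 − 1.353)/0.707 = −0.423. This gives 33.6% and Φ(−0.423 − 1.913) = 0.98%.

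**2. Vary the timing.** Fifty completers at 30% drop-out means 50/0.70 ≈ 71 randomized, so t ≈ 0.714. Entries are effect / no effect.

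| Look | 80.2% power | 77.2% power |
|---|---|---|
| t = 0.50 | 0.65% / 31.0% | 0.98% / 33.6% |
| tuned to 37.0% under no effect | 0.88% / 37.0% (t = 0.53) | 1.14% / 37.0% (t = 0.52) |
| 50 completers, t = 0.714 | 3.5% / 71% | 4.5% / 72% |
| tuned to 4.6% under the effect | 4.6% / 78% (t = 0.76) | 4.6% / 73% (t = 0.72) |
| **Section 9.9** | **4.6% / 37.0%** | **4.6% / 37.0%** |

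Each stated figure can be reached alone. No single timing reaches both.

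**3. A check free of the 10% cut.** For any fixed cut on an interim Z with unit variance, z(P no effect) − z(P effect) = θ√t. The stated pair gives −0.332 + 1.685 = 1.353; half the information needs 1.99 (80.2%) or 1.91 (77.2%). With an assumed 1,000 replicates, the standard errors are 0.66 points on 4.6% and 1.53 points on 37.0%. Moving both figures 1.96 standard errors in the helpful direction raises the gap only to 1.58.

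**4. Simulation of the planned model structure.** Set-up: 14 log-normal days, correlation 0.8, 30% drop-out, unstructured covariance, day-specific treatment differences averaged, no baseline covariate. The CV (0.75-0.85 in one set of runs) and a flat daily mean are assumptions.
- Design-drift formula, 79-80% power, 25-27 per arm: 0.6-1.2% / 33-43%.
- Look tuned to about 37% under no effect: 1.0-1.5% with the effect at 81% power, 1.5-2.7% at 75%.
- Observed standard error: no more than about 1% with the effect, and 14-29% under no effect.
- 36 per arm (50 completers): 2.8-4.0% with the effect and 64-73% under no effect.

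These inputs match Table 7 only roughly (at CV 0.75 the worst cell is 4.0 standard errors off), so the simulations illustrate and steps 1 to 3 carry the point.

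**5. The power fall.** If the assumed effect is true and conditional power is computed correctly, fewer than 10% of stopped trials would have gone on to win. Stopping 4.6% should therefore cost at most 0.10 × 4.6 = 0.46 points. The stated fall is 80.2 − 77.2 = 3.0 points. If the two powers came from separate 1,000-replicate runs, the standard error of the difference is √(0.802·0.198/1000 + 0.772·0.228/1000) = 1.8 points, so the fall is about 1.6 standard errors and may be noise.

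**The case against.** A reader might infer that the two probabilities cannot both be right for any test with correct standard errors. The documents do not support that. Step 3 covers only a fixed cut on Z. If conditional power takes its noise level from the interim data, stopping is no longer a fixed cut, and Section 9.9 gives no formula that rules this out.

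One such rule comes close. Conditional power is computed from the interim placebo variance alone, with the treated variance set at 2.25 times placebo (a 50% increase at constant CV). On subject means:
- 27 per arm: 4.3% / 37.5%, power 80.2% without the look.
- 26 per arm: 4.1% / 35.9%, power 77.7%.

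In the planned model structure, 26 per arm gave 3.8% / 35.4% at 78.9% power. Null rejection was 5.0% throughout. This part of the objection stands. Its limits are that the formula is unusual and unstated, and that it did not match the correlation 0.6 figures (2.2% / 28.3% at 86% power).

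A second route is unstructured covariance with one constant treatment effect and no small-sample correction. With the design-drift formula at 25 per arm it gives 4.2-5.7% / 36-39%. It lacks the planned treatment-by-day interaction and rejected 8.9-10.7% of null trials. A reader might infer that the sponsor simulated this model, since Section 9.1 speaks of a constant effect. That wording describes the assumed effect, not the fitted model, so this is only a possible cause.

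It is also fair that the means and variances come from external data not shown, and that the DMC procedure sits in a charter that is not part of these documents.

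**Conclusion.** The concern holds in limited form. At correlation 0.8 and 77-80% power, the usual formulas (design drift, or planned effect with the pooled interim standard error) do not give 4.6% and 37.0% together at about half the information. The stated 4.6% is roughly four or more times what they give. At 50 completers, every calculation tried stops about 63-73% of null trials. That range assumes the protocol's 30% drop-out; with less drop-out the look moves back towards half the information.

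The documents do not show which figure is wrong, or why. The power fall in step 5 is supporting evidence only, and no claim is made for correlation 0.6.

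The consequences are modest. The rule is non-binding, a futility look does not inflate type I error, and N = 100 rests on Table 7. If 4.6% is too high, it errs on the cautious side. The larger practical gap is the chance of stopping an ineffective drug, which may be well above 37% with the look at 50 completers.

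**What to change.** Rerun the Table 7 and Section 9.9 scenarios on the same replicates (10,000 or more), with and without the look. Use the planned model with its treatment-by-day interaction, the standard-error and degrees-of-freedom method of the final analysis, the conditional-power formula the DMC will use, and the look timed as it will be applied. State all of these in Section 9.9, with the number of replicates and the simulated rejection rate under no effect, so that a reader can see the test is near 5%.

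Replace the Section 9.9 power and futility probabilities where the rerun differs. Label the power in the synopsis and Section 9.1 as without the look, with the rechecked with-look figure beside it; 77.2% should not be carried over before it is rechecked.

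The cost is simulation time and perhaps slightly different stated figures. No extra patients and no design change are needed.
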